Reaching Out to Distressed Residents, Fellows, and Faculty through the Resident and Faculty Wellness Program Interacting Screening Program

NCT02010866

4/27/24

"Reaching Out to Distressed Residents, Fellows, and Faculty through the Resident and Faculty Wellness Program Interacting Screening Program"

Short Title: Reaching Out

IRB #00009003

Principal Investigator: [name]

Co-Investigators: [name], [name], [name], and [name]. (statistician)

Sponsor: OHSU (Graduate Medical Education)

Purpose/Aims:

A recent survey of 7000+ US physicians indicated that almost half of all physicians are struggling with clinical levels of burnout, 38% with clinical depression, and 6% with suicidal ideation in the past 12 months (Shanafelt et al., 2012). Similar rates of burnout and distress are present among medical trainees (e.g., Prins et al., 2007; Schwenk et al., 2010). Patient care, physician-patient communication, and physician career satisfaction and retention are negatively impacted by untreated physician distress (e.g., Wallace et al., 2009). Of particular concern, rates of suicide among male physicians are somewhat higher than males in other professions and are at least 2 times higher among female physicians when compared to their nonphysician female counterparts (Center et al., 2003; Schernhammer, 2005). US physicians who killed themselves were unlikely to have received adequate treatment for their depression and/or substance abuse—even though they had health insurance and presumably knew about appropriate interventions for mental health problems (Gold et al., 2012). Many medical trainees and physicians in practice appear to avoid counseling or taking psychiatric medication due to concerns about possible stigma, confidentiality/privacy, cost, accessibility/time, reportability to state licensing/credentialing bodies, and helpfulness of counseling with their stressors (Guile et al, 2010; Givens Tija, 2002).

In 2004, OHSU Resident Wellness Program was created to address and remove known barriers to medical residents and fellows receiving counseling and psychiatric medication services. On-site, quickly accessible, free, confidential counseling was provided by clinicians expert in treating medical providers. Educational outreach efforts to clarify that counseling is not reportable to state medical boards—impairment is reportable—were conducted with faculty and medical trainees. In presentations to trainees, faculty and faculty leaders, RWP clinicians described how counseling was helpful to many of their colleagues and how normal and appropriate this level of self-awareness and self-care are for health care providers. The utilization rate of the Resident Wellness Program in 2004-05 was 6% of all residents/fellows and then rose to 17% of residents/fellows in 2012-2013—suggesting that the program was reaching a larger group of distressed medical trainees. Several years ago at the request of faculty members, the program was expanded to include offering services to full-time SOM faculty and was renamed the Resident and Faculty Wellness Program (RFWP). Faculty utilizations rates have yet to be evaluated.

Two years ago Ey and colleagues (2013) conducted an anonymous, online questionnaire of OHSU residents and fellows (response rate of 71%) and found most residents/fellows knew about the program and were “somewhat to very likely” to access the RFWP if needed. Thirteen percent of the residents and fellows, however, indicated that they would be unlikely to access services if they were distressed. When all trainees were asked about possible barriers to accessing counseling, fewer were concerned about stigma, confidentiality, reportability, and helpfulness than medical students and residents surveyed in other academic medical centers (e.g., Guile et al., 2010; Givens Tija, 2001) but perceived barriers to counseling were reported by at least 20% of the trainees. Being uncertain about how to take time out of duty hours to come for an appointment continued to be the largest interfering factor with accessing the RFWP—especially among women and primary care residents. By contrast, ethnic minority residents and male residents expressed more concerns about whether counseling would be helpful in addressing residency/fellowship related stressors (Ey, [name], Kinzie, Choi & Girard., 2013). Although the RFWP staff have tried to address these concerns each year through orientations to new trainees and faculty and workshops to various residency programs and departments, there appear to be a group of residents, fellows, and probably faculty (they were not included in this 2011 survey) who continue to be uncomfortable and/or unwilling to seek professional help if distressed.

Following the suicide of a female resident two years ago at OHSU, the RFWP staff searched for additional ways to reach residents and faculty who continue to be unaware of the seriousness of their level of distress and risk and/or to be highly concerned about possible barriers to treatment. Of note, in the general population, the most distressed patients typically report the greatest concerns about seeking mental health treatment (Kushner Sher, 1989). Most patients who died due to suicide met criteria for a psychiatric diagnosis at the time of the suicide (Hirschfeld et al, 1997) and most college students who killed themselves were unlikely to have been in treatment at the time (e.g., Gallagher, 2005) . Although population wide screening for suicidal ideation may not directly prevent suicide, screening for risk factors for suicide (e.g., prior attempts, current depression and substance abuse), is associated with increased likelihood to receive treatment and may prevent more negative outcomes (Gaynes et al., 2004).

According to theories such as motivational interviewing and stages of change (Prochaska et al., 1992; Vogel et al., 2007), individuals change health behaviors when the benefits (e.g., being less stressed) outweigh the risks (e.g., concerns about confidentiality of treatment). Educational programming to promote the benefits and counter the perceived risks of counseling did increase adults’ motivation to get professional help (Vogel et al., 2007). Distressed physicians’ motivation to seek help following an educational intervention has not been evaluated but organizations such as the American Foundation for Suicide Prevention, ACGME (2012), and the AMA (2011) have developed policies and programming to educate physicians about the importance of treating depression and reducing suicide risk in themselves and their colleagues.

A “best practices” suicide prevention program in 50+ US universities, the American Foundation for Suicide Prevention’s Interactive Screening Program (ISP), was identified by the RFWP clinicians as a possible avenue by which to reach distressed OHSU trainees and faculty and encourage them to get help. The “Stress and Depression Questionnaire” is an anonymous, online screening tool for stress,

depression, substance abuse, eating disorders, and suicide risk. Responses are scored and ranked according to level of distress and risk with Tier 1 representing “high risk, high distress” and Tier 2 “moderate distress, less risk” and Tier 3 “low or no distress or risk”. RFWP clinicians will monitor responses, provide prompt communication back to the participants with information about how they scored, resources available to them, address any questions/concerns they might have and invite them to set up an appointment at the RFWP (if distressed). A similar size academic medical center to OHSU, UCSD, administered this survey to all medical students, residents, fellows, and faculty (13% completed it) and the majority eventually seen by clinicians indicated that they never would have sought help if they had not received feedback on the ISP and been encouraged to come in for evaluation/treatment (Moutier et al., 2012). Being able to anonymously dialogue with a clinician about their specific situation and questions appeared to persuade some participants to come in for an evaluation or accept a referral. This academic medical center did not have an in-house counseling program for residents and faculty like the OHSU RFWP—UCSD trainees received an initial evaluation from a clinician and then were provided with community referrals. Their participation rate of 13% is similar to rates of participation in the ISP in undergraduate populations (e.g., Haas et al., 2008). We hypothesize that our highly visible and utilized RFWP may lead to a higher ISP participation rate among the residents, fellows, and faculty.

Although the ultimate goal is to save lives (i.e., reduce the rate of suicide among medical trainees and faculty), the low base rate of suicide in a population (Rodgers et al., 2007) does not allow us to evaluate whether the implementation of the ISP at OHSU will lead to a drop in suicide rates at our institution. Even using patient suicidal ideation and attempts as outcomes is problematic as this information can be difficult to gather unless the patient is actively involved in treatment at the time. Rather in the present study we propose to measure the effectiveness of our suicide prevention program by trying to measure proxy variables to suicide risk—increasing protective factors and decreasing risk factors (Goldney, 2005). Specifically, we are seeking to decrease known risk factors (e.g., identify and intervene with untreated depression, substance abuse, high level of stress) and increase protective factors (e.g., promote self-awareness, receipt of support and resources and delivery of mental health services if needed).

Our aims are to:

- reduce known risk factors of untreated psychological distress (e.g., depression, high stress level, substance abuse) by encouraging all residents, fellows, and SOM faculty to complete a self-assessment of their level of stress and risk using the ISP and then offer professional help through a personalized message/dialogue that directly addresses any concerns/barriers about seeking help at the RFWP and offers resources for better coping;
- increase self-awareness in mildly/moderately distressed trainees and faculty who fill out the ISP and offer preventive/early intervention educational resources via the ISP on topics that are relevant to them (based on their responses);
- evaluate whether all RFWP patients (ones who come to the program via ISP and other referral sources) report decreased psychological distress, burnout, and risk of suicide across treatment;

- asses RFWP participants' levels of psychological distress, flourishing, burnout, and risk of suicide across treatment;
- assess at intake whether intent to quit medicine, training program or faculty position within the next 12 months is associated with level of client's distress, burnout, demographics and is a factor in seeking treatment;
- assess level of satisfaction with the RFWP educational outreach workshops, consultation to department leaders (and referral of their trainees and/or faculty), and clinical services provided to distressed trainees and faculty.

Research Questions:

1. How many trainees and faculty participate in the online, anonymous ISP survey and review the clinician's response to their surveys? In addition, how many highly distressed/high risk (Tier 1) trainees and faculty communicate anonymously with the RFWP clinician (via the dialogue function) and accept referrals or come in for an in-person evaluation?
2. How representative are the ISP participants of the overall OHSU population of SOM trainees and faculty, Providence and Legacy residents that could have participated?
 - a. Hypothesis: we hypothesize a greater overall participation rate from OHSU, Providence, and Legacy trainees and OHSU faculty than seen with UCSD SOM (13%) due to our greater utilization rate at the RFWP, and visibility as an on-site program and the higher response rate to our 2011 anonymous survey (71% among residents/fellows). We are uncertain how many Tier 1 respondents will communicate with our clinicians and agree to services—this question is exploratory.
 - b. Exploratory question re: representativeness—we hope that our participants will be similar to the overall Providence, Legacy and OHSU population so that results will be more generalizable.
3. What is the relationship among level of distress (ISP tiers), type of symptoms reported on ISP and willingness to seek treatment? Is participation in the ISP (as reported in 1st session intake questionnaire) related to response to treatment (change in distress and burnout ratings and risk level, attendance of sessions)?
 - a. Hypothesis: level of distress/risk on the ISP will be positively related to greater willingness to accept referrals or make appointment . We are uncertain if participation in the ISP per self-report on intake paper work will led to different treatment response than others seen at our program. We are uncertain whether respondents with certain symptoms (e.g., substance abuse, suicide risk) may be anxious about communicating with us and to come in for an in-person meeting—this question is exploratory.
4. How helpful were components of the ISP (getting feedback on level of distress, being able to dialogue with clinician re: concerns, and having specific resources offered) according to participants in the ISP who came for initial intake at RFWP?

- a. Prior ISP studies with undergraduate and graduate samples (e.g., Haas et al., 2008) would suggest that the online dialogue with a clinician re: concerns will be rated as especially helpful and instrumental to ISP participants who eventually sought treatment.
- 5. How many residents, fellows, and faculty show significant change in their levels of distress and burnout while in treatment at the RFWP? What demographic variables (gender, ethnicity), training/work variables (trainee/faculty status, type of program, year of training) are associated with change in distress and burnout ratings across treatment?
- 6. Is dose of treatment (# of sessions over 12 month period) associated with lower risk of quitting training program, leaving faculty position or leaving clinical medicine as a field?
- 7. At intake, what is the association between descriptive variables (i.e., demographics, programmatic factors), level of distress, burnout, and intent to quit medicine and/or training program or faculty position? Is dose of treatment (number of sessions over a 12 month period) associated with lower risk of quitting training program or faculty position?
 - a. Questions about intent to quit will be based on Boroff et al. measure used by employers and now being used in healthcare setting (e.g., OHSU Pulse Survey).
 - b. Status in training program, faculty position will be based upon clinician rating in last session.
- 8. How do consumers of RFWP services compare to the overall Providence, Legacy and OHSU population of trainees and SOM faculty in terms of demographics, program type? Are they representative?
 - a. Hypothesis: This first question is exploratory as little research exists on specific rates of recovery (e.g., decrease in distress) in health care providers in counseling/coaching. In general outpatient clinics, there are no gender or racial/ethnic differences in response to high quality mental health services (e.g., Lambert , 2007).
 - b. Hypothesis: the 2nd question—prior studies with a general population would suggest that women and primary care physicians, will be more likely to have sought counseling.
- 9. What is the level of client satisfaction reported by trainees and faculty seen for individual treatment at the RFWP or department leaders who have consulted with the RFWP staff re: referrals?
 - a. Hypothesis: this question is exploratory.

Procedures

ISP Protocol: The OHSU, Providence, and Legacy SOM leadership will announce to the SOM faculty, residents, and fellows and Providence and Legacy residents that the “Stress and Depression Questionnaire” (ISP) is now part of Providence’s and OHSU’s commitment to promote the well-being of trainees and faculty. Note: effective 7/1/21, Legacy residents/fellows will no longer be seen through RFWP so they will no longer be invited to enroll in this study. Throughout the year, the RFWP clinicians will visit SOM departments/program to introduce the ISP and present a 45-60 minute workshop/Grand Rounds on stress and depression in health care providers. Shortly after each presentation to a department, an email invitation (with a link to the secure ISP website) will be sent to all faculty,

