RFWP Client Outcomes Protocol: After completing (1.) an informed consent to be in treatment at the RFWP and (2.) a research consent form, all patients being seen at the RFWP (referred by ISP, other referral sources or self-referred) will be asked to complete a brief measure of a level of distress, burnout, level of risk and treatment history and needs. Specifically, the ACORN (a psychometrically sound, standardized 13-item measure of psychological distress within the past 2 weeks) and 2 screening questions for emotional exhaustion and depersonalization from the Maslach Burnout Inventory (MBI) will be given at the first session and subsequent sessions to measure client progress in treatment. The Maslach Burnout Inventory (MBI) is a psychometrically sound measure often used with health professionals; West and colleagues (2009) found that 2 items are highly predictive of physician burnout as a quick screen. Clinicians will review with their patients how they responded to these questionnaires—as one indicator of their response to treatment. This type of regular brief assessment and collaborative discussion with patients about their progress in mental health treatment has been shown to be highly effective in preventing patients from prematurely terminating from treatment and in facilitating the delivery of tailored, relevant interventions with patients (e.g.,<https://psychoutcomes.org>; Lambert, 2004). Patients will also complete the Flourishing Scale (a positive psychology measure that asks about whether patients feel their activities are meaningful, whether they feel optimistic about their future, feel respected). This measure is correlated with life satisfaction.

Patients also will be invited out to fill out a psychometrically sound measure of patient satisfaction, the Client Satisfaction Questionnaire (CSQ-8; Atkinson, 1979) on their level of satisfaction with services at the RFWP. They will be asked to fill the CSQ-8 out anonymously and mail back the survey or put it in a locked drop box in the waiting room areas.

Note: At the time of treatment, clients will be asked if they completed the ISP and whether it was helpful to get feedback on their level of distress and to be able to dialogue with a clinician. **Data Collection**

Sample and Measures

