ISP Sample of Residents, Fellows, and Faculty: All OHSU residents and fellows (approximately 800 annually) and all full-time (0.5 FTE) faculty (approximately 3000) will be sent via OHSU email a link to the ISP survey following the RFWP clinician's presentation of the Stress and Depression workshop to their department. Note: only residents, fellows and full-time SOM faculty will be included as they are the only ones who are eligible for services through the RFWP (we don't have capacity to provide services to all adjunct faculty). All Legacy residents (approximately 90 a year) will be invited by RFWP clinicians (during workshops/orientation to these groups) to participate in completing the ISP. Note: new Legacy residents/fellows effective 7/1/21 will no longer be enrolled. All Providence residents (approximately 90 a year) will be invited by RFWP clinicians (during workshops/orientation to these groups) to participate in completing the ISP. *RFWP Client Outcomes Sample:* All patients seen at the RFWP (to start with IRB approval) will be invited to participate in the research study—estimated to be 200-300 annually that are seen at the program. This estimate is based on 17% of 800 OHSU residents/fellows and approximately 2% of 3000 SOM faculty utilizing services through the RFWP in 2012-13. Increased outreach efforts through this proposed project “Reaching Out” will likely raise the visibility of the RFWP (especially among faculty) and lead to a slightly higher number of faculty and medical trainees utilizing future RFWP annually.

All clinical data are entered into an encrypted ACCESS clinical records database that only RFWP clinicians have permission to access. Participants who also complete the Research Study Consent Form will have the following clinical data exported into a research database for analyses: RFWP Subject ID number* randomly assigned (by computer) to the resident, fellow, or faculty member at time of intake,

- demographic and work/training program information (gender, year of birth, ethnic/race, year of training if relevant, resident/faculty status, type of program/specialty) from the “Personal History and Data Form” completed by the patient in the first meeting
- reason for referral, referral source, knowledge of RFWP
- psychological, suicide, and medication history (if relevant) based on clinical interview
- participation in the ISP and ratings of helpfulness of the ISP components (in “Personal Health History and Data Form”)

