Statistical analyses will be conducted by [name] and her research team and will consist of descriptive analyses (e.g., frequencies, means, standard deviations), correlational analyses, and some multiple regression analyses to determine whether participation in the ISP is predictive of engagement in treatment and recovery from depression, substance abuse, or suicide risk. In addition, pre-post comparisons of risk, distress and burnout levels will be conducted in relation to demographic and treatment factors for all participants in the RFWP. Additional analyses will be conducted comparing participants to overall Providence and OHSU SOM populations on demographics to see if samples are representative of their institution's eligible population.

References

ACORN, Collaborative Outcomes Resource Network. <https://psychoutcomes.org>.

Accreditation Council for Graduate Medical Education. ACGME institutional requirements.

http://www.acgme.org/acgmeweb/Portals/0/irc_IRCpr07012007.pdf. Updated 2007. Accessed November 4, 2012.

American Medical Association. Physician suicide webinars. <http://www.ama-assn.org/pub/physician-resources/physician-health/physician-suicide>. Accessed 11/20/2011.

Boroff, K. E., & Lewin, D. (1997). Loyalty, Voice, and Intent to Exit a Union Firm: A Conceptual and Empirical Analysis. *Industrial and Labor Relations Review*, 51(1), 50-63.

Drum, DJ et al. New data on the nature of suicidal crises in college students: Shifting the paradigm. *Professional Psychology*. 2009; 40, 213-222.

Ey S, [name] M, Kinzie JM, Choi D, Girard DE. "If you build it, they will come": Attitudes of medical residents and fellows about seeking services in a resident wellness program. *JGME*. 2013 (Sept).

Gallagher RP. *National Survey of Counseling Center Directors*. Monograph Series Number 80. Alexandria, VA: International Association of Counseling Services. 2005.

Gaynes BN et al. Screening for suicide risk in adults: A summary of the evidence for the US preventive services task force. *Ann Intern Med*. 2004; 140: 822-835.

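### Uncontrolled pre-post change in clients is offered as one strand of evidence on the program's effectiveness, which the design cannot support; the claim should be limited to description

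*Protocol*

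**What the plan says.** The Purpose/Aims section explains that suicide is too rare to serve as an outcome at one institution, and continues: "we propose to measure the effectiveness of our suicide prevention program by trying to measure proxy variables to suicide risk". It then names the proxies as lower risk factors and higher protective factors. These include finding and acting on untreated distress, raising self-awareness, and delivering support and services.

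One of the aims that follow is to evaluate whether all clients of the Resident and Faculty Wellness Program (RFWP), whatever their referral source, "report decreased psychological distress, burnout, and risk of suicide across treatment". Research Question 3 groups change in distress, burnout and risk level, together with attendance, under the label of response to treatment. The Statistical Analyses section says that "pre-post comparisons of risk, distress and burnout levels will be conducted in relation to demographic and treatment factors for all participants in the RFWP".

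On who is measured and when:

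- **Sample and Measures:** "All patients seen at the RFWP (to start with IRB approval) will be invited to participate in the research study".
- **RFWP Client Outcomes Protocol:** the distress measure (ACORN, covering the past 2 weeks) and two burnout items "will be given at the first session and subsequent sessions to measure client progress in treatment".
- **ISP Protocol:** after the online Interactive Screening Program (ISP), Tier 1 and Tier 2 respondents are urged to come in, and Tier 3 respondents may be offered a meeting. Clients may also refer themselves or come from other sources.

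**The concern.** People tend to seek counseling, or to be urged towards it by a screening result, when their distress is higher than is typical. A score taken at that moment is expected to be lower later on average, even if nothing is done. Part of this is chance fluctuation in the score and part is natural recovery from a bad period.

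Within-client change in a single treated group contains both of these along with any effect of the program, and nothing in the plan separates them. Describing such change is legitimate. The difficulty arises when it is placed under a purpose of measuring effectiveness and labelled as response to treatment. A fall in ACORN or burnout scores could then be read as evidence that the program works, when the same fall might have occurred without it.

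**Working it through.** **1. Is there a comparator for change?**

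| Possible comparator | What the protocol provides | Usable? |
|---|---|---|
| Untreated or delayed group | None; the outcomes sample consists of patients seen at the RFWP | No |
| Institutional summary data | Headcounts, sex, ethnicity, age, specialty group | No, there are no outcome scores |
| ISP versus non-ISP clients | Self-reported, not randomised, both treated | No, not for a program effect |
| Number of sessions | Not randomised, all treated | No, not for a program effect |

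The text mentions neither regression to the mean nor natural recovery, and does not limit pre-post change to description.

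**2. Which strands are affected?** Participation, dialogue, referral uptake, helpfulness ratings and satisfaction are not change scores from a baseline taken at help-seeking, so the artefact does not touch them. The affected strand is pre-post change in distress, burnout and risk.

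**3. The protocol's own figure.** It gives no SD, correlation or effect size for change. Its one relevant figure is the sample of 200 to 300 clients a year, based on 2012-13 use: 0.17 × 800 + 0.02 × 3000 = 136 + 60 = 196. This agrees with the lower end.

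**4. Expected fall with no program effect.** Let z be the mean intake excess above the population mean in SD units, and r the first-to-last correlation that would hold without treatment. Assume the same mean and SD at both times, and that entry is related to the later score only through the intake score. Then

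expected fall = (1 − r) × z

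| | z = 0.5 | z = 1.0 | z = 1.5 |
|---|---|---|---|
| r = 0.6 | 0.20 | 0.40 | 0.60 |
| r = 0.7 | 0.15 | 0.30 | 0.45 |
| r = 0.8 | 0.10 | 0.20 | 0.30 |

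Both inputs are assumptions.

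**5. Wider check, using the trainee utilisation rate.** If the 17% of trainees who attend were selected on a variable with correlation e to distress, the mean intake excess is e × φ(z₀.₈₃)/0.17 = e × 1.49. This is 0.45 SD at e = 0.3, 0.74 SD at e = 0.5 and 1.49 SD at e = 1. For 136 clients, all with a later score, the SD of change is about √(2(1 − r)). The chance of a two-sided p < 0.05 from this artefact alone is about Φ(fall × √136 / √(2(1 − r)) − 1.96).

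| e | Fall in SD at r = 0.5 / 0.7 / 0.9 | Chance of p < 0.05 at r = 0.5 / 0.7 / 0.9 |
|---|---|---|
| 0.3 | 0.22 / 0.13 / 0.04 | 74% / 52% / 21% |
| 0.5 | 0.37 / 0.22 / 0.07 | 99% / 92% / 49% |
| 1.0 | 0.74 / 0.45 / 0.15 | about 100% / about 100% / 97% |

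The values of e and r are assumed. The result depends heavily on them.

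**The case against.** The strongest reply is that the sentence on effectiveness concerns the suicide prevention program, which the Purpose/Aims section introduces as the ISP, and that it goes on to define its proxies largely as identification and service delivery. The pre-post aim covers all RFWP clients from any source. The aims and Question 5 speak of change across or during treatment, recovery rates are called exploratory in the hypothesis under Question 8, and no planned analysis announces a causal conclusion. On this view the issue is one loose word in an openly observational evaluation.

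Part of this stands. A reader might infer that the whole case for effectiveness rests on pre-post change; it does not. A reader might also infer that the protocol commits itself to reporting any fall as a program effect; it does not say so. Even so, decreasing risk factors is among the named proxies, the aim on decreased distress follows directly, and Question 3 itself calls within-client change a response to treatment. The causal reading is therefore invited by the text, and nothing in the text limits it.

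Two further inferences are tempting and are not supported:

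- **That a significant fall is almost guaranteed.** Entry has no distress threshold, since self-referral is open and Tier 3 respondents may be offered a meeting. The chance falls to 21% in the mildest case above.
- **That ISP-route clients would appear to respond best.** They are flagged earlier and on a different instrument (PHQ-9 and suicide-risk tiers), so some regression may occur before the first ACORN score. Their intake severity relative to other clients is not stated, and the protocol itself declares uncertainty about whether their response will differ.

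**Conclusion.** The concern holds for the pre-post strand only. As designed, change in distress, burnout and suicide risk among clients cannot distinguish a program effect from regression to the mean or natural recovery, so it should not stand as evidence of effectiveness.

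The size is not computable from the protocol. With an intake excess of 0.5 to 1.5 SD above the population mean and a first-to-last correlation of 0.6 to 0.8, the expected fall without any effect is about 0.1 to 0.6 SD. It would be smaller if many clients enter with ordinary levels of distress, or if their distress is long-standing and not a passing peak. This is a matter of what is claimed, and no number in the protocol is wrong. It is worth correcting in the protocol itself because it sits in the stated purpose and in a research question, where a later analysis plan would not remove it.

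**What to change.** Three changes of wording:

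1. In Purpose/Aims, replace the phrase about measuring the program's effectiveness with wording such as: describe reach, service uptake and change in risk and protective factors among users of the program.
2. In Purpose/Aims and in Statistical Analyses, state that pre-post change is descriptive and will not be reported as a program effect.
3. In Research Question 3, replace *response to treatment* with *change during treatment*.

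No control group, new data or extra analysis is required. The cost is a more modest stated aim.

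Taking the second session as baseline might look like a remedy, but it is not one. ACORN covers the past 2 weeks, so the second score may reflect the same episode; natural recovery remains; and clients seen only once are lost. Showing change by intake severity would display the artefact itself.
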